4.7 Medical History and Concomitant Illnesses

Medical and surgical history (presented together) and concomitant illness will be listed by subject including treatment, description of the disease/procedure, MedDRA System Organ Class (SOC), MedDRA preferred term, start date and stop date (or ongoing if applicable) based on the FAS.

A summary of the number and percentage of subjects with any relevant medical history, surgical history and concomitant illness will be summarised based on the FAS for each study Part by each dose level of AZD1402, placebo and pooled AZD1402 and overall, by SOC and preferred term.

4.8 Prior and Concomitant Medications

Prior medication stopped prior to the first dose of IP (exclusive), as well as all concomitant medications taken during the conduct of the study will be described.

Prior and concomitant medication will be coded according to the World Health Organization Drug Dictionary (WHO-DD), version March 2020 or later.

Medication start and stop dates will be compared to the date of first dose of study medication to allow medications to be classified as either prior only, both prior and concomitant, or concomitant only. Medications starting after the completion + 4 days/discontinuation of the treatment/will be listed but will not be classified or summarised.

Medications that started and stopped prior to the first dose of IP (exclusive) will be considered as prior medications. Any medication or vaccine (including over the counter or prescription medicines, vitamins, and/or herbal supplements or other specific categories of interest) that starts after first dose of IP will be recorded as concomitant.

If a medication starts prior to the first dose of IP and continued on or and stops after first dose of IP then the medication will be classified as both prior and concomitant. Medications will be classified as concomitant only if they have a start date on or after first dose of IP and during the study conduct (including Follow-up Period).

If medication start and/or stop dates are missing or partial, the dates will be compared as far as possible with the date of the first dose of IP. Medications will be assumed to be concomitant only, unless there is clear evidence (through comparison of partial dates) to suggest that the medication started prior to the first dose of IP. If there is clear evidence to suggest that the medication started prior to the first dose of IP, the medication will be assumed to be both prior and concomitant, unless there is clear evidence to suggest that the medication stopped prior to the first dose of IP. If there is clear evidence to suggest that the medication stopped prior to the first dose of IP, the medication will be assumed to be prior only.

Prior and concomitant medications will be listed by subject, treatment group, and study part and will include the following information: reported name of drug, medications or therapy, anatomical therapeutic chemical (ATC) and generic drug name, the route of administration, dose, frequency, study day of start of medication and duration, and indication.

A summary of prior medications received and concomitant medications, preferably by ATC level 4 category when possible or the highest ATC level when level 4 is not available and generic drug name, and by treatment part will be reported.

The duration will be calculated as:

- Duration (in hours) = end date/time – start date/time, in case date and time is available.
- Duration (in days) = (end date – start date) + 1, in case only date is provided.

The duration may be presented in hours or days in the listing depending on the applicability to the emerging data. For medications with partial or completely missing start date/times and/or end date/times, the duration will not be calculated.

For summary tables, multiple records for a subject in the same ATC level 4 category when possible or the highest ATC level when level 4 is not available and generic drug name will be counted only once.

4.9 Treatment Exposure/Compliance

4.9.1 Treatment Exposure

In the assessment of the treatment exposure, interruptions will be considered.

When there is no interruption treatment exposure duration (in days) will be calculated as follows:

Treatment exposure duration (in days) = min (date of last dose received, date of death, data of data cut-off) - date of first dose received) + 1.

When there is any interruption treatment exposure duration will be calculated as follows:

- for each interruption the duration of interruption will be calculated as follows:
(date of first dose received after the interruption - date of first day of interruption).
- the treatment exposure duration (in days) will be calculated as follows:
Treatment duration (in days) = (date of last dose received, date of death, data of data cut-off - date of first dose received) + 1 – (sum of interruptions).

Treatment duration of exposure (days) will be summarised per each Part by treatment for the SS, using descriptive statistics.

A by subject listing of drug administration data will be provided.

4.9.2 Treatment Compliance

Compliance will be assessed by checking the daily e-Diary and eCRF.

For all treatments, treatment compliance will be calculated as:

$$\text{Treatment compliance (\%)} = \frac{\text{Number of doses taken during treatment period}}{\text{Number of doses planned (28 days*) during treatment period}} \times 100.$$

*The number of doses planned is 55 since there is only 1 dose in the morning of Day 28.

Compliance is expected to be $\geq 80\%$ during the Treatment Period.

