1 PROTOCOL SUMMARY

1.1 Synopsis

Protocol Title: A Two-part Phase IIa Randomised, Double-blind, Placebo-controlled, Dose-ranging, Multi-centre Study to Assess Efficacy and Safety of Inhaled AZD1402 Administered as a Dry Powder Twice Daily for Four Weeks in Adults with Asthma on Medium-to-High Dose Inhaled Corticosteroids

Short Title: Efficacy and Safety of Inhaled AZD1402 administered Twice Daily for Four Weeks in Adults with Asthma on Medium-to-High Dose Inhaled Corticosteroids

Rationale:

Asthma is a chronic, complex, and heterogeneous respiratory disease characterised by a range of pathogenic features including pulmonary inflammation, mucus hypersecretion, variable airway obstruction, and airway remodelling. Symptoms and airway obstruction can resolve in response to therapy or spontaneously, but participants remain at risk of severe worsening of their asthma (exacerbations). These asthma exacerbations can be life-threatening, can significantly impact the participant's quality of life, and result in significant healthcare costs.

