^c Visit 1 can be done on several/different days prior to Visit 2.

^d Participants may be admitted on Day 27. Day 28 should be performed on the scheduled calendar day as far as possible; the -2-day window may be utilised only if required. If the -2-day window is utilised, all subsequent visits will be adjusted to follow time window between visits as specified in the SoA.

^e Discharge on Day 14 after the morning post-dose procedures.

^f Height only at Visit 1.

^g A complete physical examination including an assessment of the general appearance, respiratory, cardiovascular, abdomen, skin, head and neck (including ears, eyes, nose and throat), lymph nodes, thyroid, musculoskeletal and neurological systems will be performed.

^h A brief physical examination including an assessment of the general appearance, skin, abdomen, cardiovascular, and respiratory systems will be performed.

ⁱ Vital signs to be performed BID whilst participants are in-clinic. Vital signs will be measured pre-dose at the scheduled morning dose in-clinic visits and additionally prior to the evening dose if participants receive the evening dose at the clinic (eg, due to optional overnight stay).

^j Refresher training as required.

^k Rescue medication to be as necessary. Check if participant has enough rescue medicine for use at-home use and refill if necessary.

^l FeNO will be measured pre-spirometry, pre-dose (as applicable), and pre-bronchodilation.

- m FeNO assessments at home will only be performed (morning and evening) at non-clinic visit timepoints.

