^k Spirometry will be performed 45 minutes and 15 minutes prior to first dose of study intervention on Day 1 and pre-dose at all other visits. If possible, all post-randomisation pre-dose morning clinic device spirometry assessments should be performed within ± 1.5 hours of the time that the 15 min prior to randomisation spirometry was performed.

^l Reversibility testing will be performed 15 to 30 minutes after inhalation of 400 µg of salbutamol.

^m ECG will be measured before study drug administration on Day 1 (within 75 min), and 1 hour (± 20 min) after administration of study intervention on post randomisation visits as indicated.

ⁿ SPFQ (optional) will not be completed at unscheduled visits.

^o At-home spirometry will be completed up to V8 and only to be completed at non-clinic visit timepoints.

^p At Visit 1 the e-Diary is set up, participants perform training and ACQ-6 is completed.

q The e-Diary will be completed twice daily during the Run-in, Treatment, and Follow-up Period.

r Study intervention will be administered **CCI**

28). Date and time of administration at home will be registered in the e-Diary by the participant. Study drug administration at the clinic will be under supervision. The Day 28 dosing window \pm 2 days should only be used if needed, and where possible to keep within \pm 1 day.

s AEs will be collected from the time of informed consent. Unscheduled safety sampling may be performed at the discretion of the Investigator in the event of AEs/AESIs, including but not limited nasal swabs to confirm infection.

t Baseline safety sampling will be performed pre-dose on Day 1.

u Blood samples will be analysed for IgE if potential drug related IgE response is observed in any participant.

v Local CRP may be performed from Visit 3 and throughout the study in the event of AE/AESI as required to inform suspension/stopping criteria.

w PCR may be performed to confirm hepatitis B / hepatitis C status if required. Additional evaluation may be required in participants with any signs of active TB at the time of screening or positive interferon-gamma release assay (IGRA, QuantiFERON®-TB Gold) test according to the local standard of care.

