x Blood samples for PK measurements will be collected in all participants pre-dose at each visit, including unscheduled visits. Intense sampling may be performed in approximately 25% of participants per treatment arm (for example, 20 subjects in the **Q**mg treatment arm). Timing of intense samples: Day 1: 1, 2, 3 (\pm 10 min), 6, and 8 h (\pm 20 min), Day 21 4 h post-morning dose (\pm 20 min) and Day 28 (last dose), 1, 2, 3 (\pm 10 min), 6, 8 (\pm 20 min), 24 (\pm 2 h), 48 (\pm 2.5 h), and 96 h (\pm 2.5 h; single dose of AZD1402 only on last day of dosing). PK sampling timepoints may be amended based on results from Part 1a/b. An unscheduled PK sample may be collected in the case of AEs and / or unscheduled safety blood sampling.

y ADA sampling, pre-dose Day 1, Day 14, Day 21, Day 28, and at the Follow-up Visits. An unscheduled ADA sample may also be collected in the case of AEs/AESIs and/or unscheduled safety blood sampling.

z Sample collection only if consented. If for any reason the sample is not drawn at Visit 3, it may be taken at any visit until the last study visit.

aa Proposed samples and times: Serum: Pre-dose Day 1, pre-dose Week 2, Week 4 and at Follow-up. **CCI** Pre-dose Day 1, and Week 4. **CCI** Pre-dose Day 1, Day 28, and Day 39. **CCI** Pre-dose Day 1.

bb All urine pregnancy tests will be done pre-dose. In case of a positive result, a serum pregnancy test will be performed.

cc SARS-CoV-2 serology at Screening; PCR is optional and may be performed centrally or at the local laboratory as clinically indicated and as per local guidelines for the duration of the study. Ad hoc nasal and/or throat-swab specimen is to be collected for the identification of a suspected respiratory infection during any visit. This may be performed locally, or if required by central laboratory.

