7 DISCONTINUATION OF STUDY INTERVENTION AND PARTICIPANT DISCONTINUATION/WITHDRAWAL

7.1 Discontinuation of Study Intervention

7.1.1 Permanent Discontinuation of Study Intervention for Individual Participants (Part 1 and Part 2)

If any participant meets with any of the following criteria, then he/she will be permanently discontinued from the study intervention.

Part 1

- FEV₁ decrease $\geq 30\%$ from baseline* (as determined by pre first study intervention assessments)
 - In-clinic assessment: Stop dosing and enter participant into Follow-up.
 - Home assessment: Stop dosing and confirm spirometry results in-clinic at earliest opportunity. Enter participant into Follow-up if decline in FEV₁ confirmed (as described in the study reference manual).
 - Characterise potential reasons for the reduction in FEV₁ and determine if consistent with a hypersensitivity-like event, infection, or asthma exacerbation.
 - Participant should be followed until resolution of the symptoms and recovery or stabilisation of FEV₁.

Part 2

- FEV₁ decrease $\geq 30\%$ from baseline*
 - In-clinic assessment: Stop dosing and enter participant into Follow-up:
 - Home assessment: If $\geq 30\%$ decline is sustained over 2 consecutive assessments.
 - Assess associated symptoms and suspend dosing if clinically indicated.
 - Confirm spirometry results in-clinic at earliest opportunity. Enter participant into Follow-up if decline in FEV₁ confirmed.

- If dosing was suspended and if FEV₁ decline is not confirmed, dosing may be resumed at the discretion of the Investigator.
- Characterise potential reasons for the reduction in FEV₁ and determine if consistent with a hypersensitivity-like event, infection, or asthma exacerbation.
- Participant should be followed until resolution of the symptoms and recovery or stabilisation of FEV₁.
- Dosing may be suspended at any time for safety reasons at the discretion of the Investigator.
- Once dosing has been interrupted and resumed, should dosing be suspended again due to safety concerns, the event should be characterised and the patient withdrawn from dosing.

Part 1 and 2

- Withdrawal of consent to further treatment with study intervention.
- Lost to Follow-up.
- Acute severe hypersensitivity or hypersensitivity-like event/anaphylaxis.
- Any TESAE that is considered related to the study intervention by the Investigator.
- Pregnancy.

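### SAP 4.9.2 divides every participant's doses by 55, although the last dosing day may move within its window and dosing may be stopped or suspended under the protocol; the reported compliance percentage is therefore not a clean measure of adherence

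*SAP*

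**What the plan says.** SAP 4.9.2 opens its formula with "For all treatments, treatment compliance will be calculated as" and then divides doses taken in the Treatment Period by doses planned. A footnote fixes the denominator: "The number of doses planned is 55 since there is only 1 dose in the morning of Day 28". The section gives no rule for a shifted last dosing day, a permanent stop or a suspension. It repeats the 80% expectation of Protocol 6.4.1, where compliance is checked at each visit and a lower value leads to retraining.

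The schedules in Protocol 1.3 let the end of dosing move. In Part 2 (Table 2, study drug administration footnote), the Day 28 dosing window is ±2 days, with the instruction that the ±2 "days should only be used if needed, and where possible to keep within" ±1 day. The Table 2 PK footnote specifies a "single dose of AZD1402 only on last day of dosing", which ties the single dose to the last dosing day and not to calendar Day 28. In Part 1 (Table 1, Day 28 footnote) the window is one-sided: "the -2-day window may be utilised only if required". The SAP's own schedules (Appendix 5.1) carry the same windows. The Treatment Period ends at Visit 7 in both parts (SAP 3.1.1 and 3.1.2).

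Protocol 7.1.1 lists criteria for permanent discontinuation, and 7.1.2 lists criteria for suspension. For Part 2, 7.1.1 adds a discretionary route: "Dosing may be suspended at any time for safety reasons at the discretion of the Investigator".

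SAP 4.9.1, directly before the compliance section, says: "In the assessment of the treatment exposure, interruptions will be considered". It subtracts them from exposure duration.

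**The concern.** The numerator follows what actually happened up to Visit 7, while the denominator is a constant. Two separate things then enter a percentage that reads as adherence.

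The first is visit timing. Finishing early or late within the permitted window changes the score although no dose was missed, and in Part 2 it can push the score above 100%, for which the SAP has no rule.

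The second is treatment completion. Doses not taken after a stop or during a suspension under the protocol are counted in the same way as doses the participant skipped. Several of the triggers are safety outcomes, and these may differ between arms.

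What is at stake is how the FEV₁ and PK results are read. Readers look at compliance to judge whether drug was taken as scheduled. Here a value just above or below 80% may reflect the calendar or a protocol rule and not behaviour.

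**Working it through.** **Inputs.** Two doses per day: the Protocol 1.1 title, "Inhaled AZD1402 Administered as a Dry Powder Twice Daily for Four Weeks in Adults with Asthma" (the regimen text elsewhere is partly redacted). One dose on the last dosing day: Protocol 1.3, Table 2. Windows: Day 26 to 30 in Part 2, Day 26 to 28 in Part 1. Denominator 55 and expectation of at least 80%: SAP 4.9.2.

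**Reproducing the plan's figure.** With last dosing day D, doses due = 2 × (D − 1) + 1 = 2D − 1. For D = 28 this is 2 × 27 + 1 = 55, an exact match, which also confirms twice-daily dosing.

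**Every dose taken, last day anywhere in the window.** Reported compliance = (2D − 1) / 55.

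| Last dosing day | Doses due | Reported | Possible in |
|---|---|---|---|
| 26 | 51 | 92.7% | Parts 1 and 2 |
| 27 | 53 | 96.4% | Parts 1 and 2 |
| 28 | 55 | 100.0% | Parts 1 and 2 |
| 29 | 57 | 103.6% | Part 2 only |
| 30 | 59 | 107.3% | Part 2 only |

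Within the preferred ±1 day in Part 2 the range is 96.4% to 103.6%.

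**Around the 80% line.** 0.80 × 55 = 44 doses.
- Last day 30, 44 doses taken: reported 44/55 = 80.0%; share of doses due 44/59 = 74.6%.
- Last day 26, 43 doses taken: reported 43/55 = 78.2%; share of doses due 43/51 = 84.3%.

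So the constant can misplace a participant in either direction.

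**Permanent stop, no dose missed before it.**
- Last dose Day 14 evening: 28/55 = 50.9%.
- Last dose Day 21 evening: 42/55 = 76.4%.
- Last dose Day 22 morning: 43/55 = 78.2%; Day 22 evening: 44/55 = 80.0%.

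A stop therefore gives a score below 80% only if the last dose is no later than the morning of Day 22.

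**Suspension, no other dose missed.**
- Last day 28, 12 doses withheld (6 days): 43/55 = 78.2%.
- Last day 26, 8 doses withheld (4 days): (51 − 8)/55 = 78.2%.

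**With a participant-specific denominator.** A completer who takes every dose due scores 100% for any D from 26 to 30, with or without a documented suspension.

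**The case against.** The strongest reply is that the SAP labels the denominator as the doses planned over 28 days, so compliance may simply mean the share of the planned course. On that reading 50.9% after a Day 14 stop is the intended answer, and preferring adherence while on treatment is a choice of definition. This stands for the low scores after a stop. It does not explain 92.7% for a complete course ending on a permitted Day 26, or 107.3% for one ending on Day 30. It also sits uneasily with Protocol 6.4.1, where low compliance leads to retraining, which addresses behaviour.

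Stopping is also visible elsewhere. SAP 4.4.1 tabulates treatment completion and discontinuation with reasons, SAP 4.9.1 adjusts exposure and lists drug administration by subject, and SAP 4.17.1 summarises adverse events leading to discontinuation. A careful reader can separate the two, which limits the harm. It is also fair that the windows are for use only when needed, and that the cases near 80% are illustrations with no known frequency.

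A reader might infer more than the documents support, in three ways.
- That the visit window alone can take a fully adherent participant below 80%. It cannot: its lowest value is 92.7%, and lower scores need a stop or a suspension of several days.
- That 55 is miscounted. It is correct for a last dose on the morning of Day 28; the problem is applying it to everyone.
- That the efficacy conclusion is biased. Efficacy uses the FAS (SAP 4.5.2, 4.10), the primary model has no compliance term (4.11), the per-protocol analysis has been removed (4.20), and 4.9.2 attaches no exclusion to 80%.

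**Conclusion.** The fixed denominator does not fit the schedules it is meant to summarise. For participants who take every dose due, the permitted window gives 92.7% to 107.3% in Part 2 and 92.7% to 100% in Part 1, and participants near 80% can be placed on the wrong side of it. The mixing of adherence with completion is a separate matter of definition, which the SAP should state openly.

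The consequence is confined to a descriptive measure. No analysis set, model or test in the SAP is defined by this percentage. SAP 4.4.2 refers treatment deviations to a separate deviation specification that is not among the documents, so whether that specification uses the percentage cannot be seen.

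The figures assume twice-daily dosing up to the day before the last dosing day. For Part 1 they also assume that the single final dose moves with Visit 7 when the −2-day window is used; the Table 1 PK footnote words it as Day 28.

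**What to change.** Reword SAP 4.9.2 along these lines.
- Participants who complete treatment: planned doses = 2 × (actual Visit 7 dosing day) − 1, less doses withheld under a documented protocol-directed suspension, in line with the interruption rule in SAP 4.9.1. Name the protocol sections that qualify, and say whether the investigator-discretion route in 7.1.1 is among them.
- Participants who permanently discontinue: keep 55 and label the result as share of the planned course. Add a second, separately labelled figure for compliance up to the last dose or the discontinuation date, and state which of the two dates is used.
- Keep the 80% reference, and state which figure it applies to.

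The denominator should not simply be cut off at any permanent discontinuation. Protocol 7.1.1 includes withdrawal of consent to treatment and loss to follow-up among the reasons, so a participant who took one dose and left would score 100%.

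The cost is a few lines of SAP text and one derivation. Home dosing times are in the e-Diary, clinic doses in the eCRF, and start and stop dates and delays are already recorded (Protocol 1.3, 6.4, 6.4.2). No new data or visits are needed, and no clinical rule changes.

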4.10 Efficacy Evaluation

All the efficacy analysis will be based on FAS.

4.10.1 Analysis and Data Conventions

No statistical hypotheses will be tested in Part 1 (Lead-in Cohort) of this study. Part 2 (Main cohort) of this study aims to demonstrate that AZD1402 improves FEV₁ compared to placebo.

The null hypotheses for the primary analysis in Part 2 is that there is no difference in the change from baseline at Week 4 (Visit 7) in pre-bronchodilator in-clinic FEV₁ in AZD1402 treated participants compared to placebo-treated participants.

The following comparisons will be performed:

- AZD1402 inhalation ^{CCI} mg ^{CCI} versus placebo inhalation ^{CCI}.
- AZD1402 inhalation ^{CCI} mg ^{CCI} versus placebo inhalation ^{CCI}

4.10.2 No formal comparisons between the different AZD1402 doses will be conducted. Adjustments for Covariates

The primary efficacy analysis for Part 2 will be adjusted for the following baseline covariates:

1. Country (stratification variable)
2. Baseline FEV₁

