Section 1.1 Synopsis Section 4.1.1 Figure 3 Section 4.1.2 Section 9.2	Planned number of participants in Part 2 updated to 165 from 180. Number of participants randomised into the 20 mg arm corrected to 5 from 20	To reflect number of participants randomised prior to stopping randomisation into the 20 mg arm (reduced to 5 from 20)	Non-substantial
Section 1.1 Synopsis Section 4.1.2 Section 5.1.2	Stability of ICS-LABA dose requirement prior to Visit 1 updated from 3 months to 4 weeks	To take into account existing duration of screening and run-in period prior to randomisation	Substantial
Section 1.1 Synopsis Section 4.1.2 Section 5.1.2	Stability of additional maintenance controller medications prior to Visit 1 updated from 3 months to 4 weeks	To take into account existing duration of screening and run-in period prior to randomisation	Substantial
Section 1.3 Table 2	Footnote clarified to include information about serum pregnancy test in case of positive result of urine pregnancy test in Part 2	For verification of pregnancy status (leading to permanent discontinuation of study intervention in case of positive result)	Non-substantial
Section 4.1.2 Section 5.1.2	Removal of inclusion criterion that participant should have at least one severe asthma exacerbation in the 3 years prior to Visit 1	Amended to optimise selection of the participant population allowing participants without severe asthma exacerbations to be included in Part 2	Substantial

Section Number and Name	Description of Change	Brief Rationale	Substantial/Non-substantial
Section 4.1.2 Section 5.1.2 Section 5.1.4	Part 2-specific inclusion and randomisation criteria updated to have FEV ₁ range from 40% to 85%. Amended throughout the protocol as applicable	Amended to optimise selection of the participant population using broader FEV ₁ range inclusion criteria	Substantial
Section 4.4	Clarified definition of the end of study according to European Union and Food and Drug Administration requirements.	For consistency and alignment in terms of posting study results	Non-substantial
Section 5.1.4	Part 2-specific randomisation criterion updated minimum compliance with ePRO completion to 70%	Amended to optimize selection of the participant population using less stricter compliance randomisation criteria	Substantial

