Part 1a will consist of 30 participants who will be randomised 1:1:1 to receive 1 of the 2 [CC1] AZD1402 DPI doses ([CC1] mg) or placebo in parallel. Part 1b will consist of 15 participants who will be randomised 2:1 to receive the [CC1] AZD1402 DPI dose ([CC1] mg) or placebo. Due to logistical reasons, the randomisation in Part 1 will be stratified by site in Australia and Germany.

Part 1a Lead-in Cohort

- AZD1402 inhalation [CC1] mg [CC1]
- AZD1402 inhalation [CC1] mg [CC1]
- Placebo inhalation [CC1]

Part 1b Lead-in Cohort

- AZD1402 inhalation [CC1] mg [CC1]
- Placebo inhalation [CC1]

Part 2

Part 2 will be randomised, double-blind, placebo-controlled and will include approximately 165 participants to evaluate 2 inhaled dose levels ([CC1] mg and [CC1] mg) of AZD1402 against placebo. Approximately 5 participants will be randomised to [CC1] mg and 80 participants per arm will be randomised to [CC1] mg and placebo, respectively. The number of subjects enrolled in the [CC1] mg dose will depend on the enrolment rate and the randomisation ratio will change during the study. Patients will be randomised 2:1 (active to placebo) whilst the [CC1] mg arm is ongoing. Once the [CC1] mg has stopped recruiting and randomisation continues in the [CC1] mg and placebo arms, the randomisation ratio will be 1:1 (active to placebo). Adult participants (age 18 to 75 years, inclusive) with physician-diagnosed uncontrolled asthma treated with medium-to-high dose ICS (total daily dose > 400µg of budesonide dry powder formulation or equivalent) with LABA, as maintenance treatment, for at least 6 months prior to Visit 1 will be included. ICS-LABA and any additional asthma maintenance controller medications (eg, leukotriene receptor inhibitors, theophylline, long-acting muscarinic antagonist [LAMA], and chromones) must be stable for at least 4 weeks prior to Visit 1.

Apart from the scheduled clinic visits, the 4 weeks of dosing in Part 2 of the study will be at home. Part 2 will be started after the unblinded safety review for Part 1a. Part 2 will include:

- AZD1402 inhalation [CC1] mg [CC1]

- AZD1402 inhalation ^{CC1} mg [REDACTED]
- Placebo inhalation ^{CC1} [REDACTED]

Participants in both parts of the study will receive a handheld e-Diary device which they are required to complete twice daily during the entire duration of the study.

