9 STATISTICAL CONSIDERATIONS

9.1 Statistical Hypotheses

No statistical hypotheses will be tested for in Part 1 (Lead-in Cohort) of this study.

Part 2 (Main Cohort) of this study aims to demonstrate that AZD1402 improves FEV₁ compared to placebo.

The null hypotheses for the primary analysis in Part 2 (Main Cohort) are that there is no difference in the change from baseline at Week 4 in FEV₁ in AZD1402 treated participants compared to placebo-treated participants. The following comparisons will be performed:

- AZD1402 inhalation CCI mg CCI versus placebo inhalation CCI
- AZD1402 inhalation CCI mg CCI versus placebo inhalation CCI

No adjustments for multiple testing will be performed.

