4.19 Determination of Sample Size

In Part 1 (lead-in cohort), approximately 45 participants will be randomised. Part 1a will consist of 30 randomised participants and Part 1b will consist of 15 randomised participants. The sample size for Part 1 (lead-in cohort) is not based on any sample size calculation but was chosen to obtain reasonable evidence of safety and tolerability without exposing undue number of participants to the study intervention. In Part 2 (main cohort), 73 evaluable participants per treatment arm (████ mg and placebo) will provide █████% power using a 1-sided test and 5% significance level to detect a difference of 175 mL in FEV₁ between AZD1402 versus placebo. This is based on a SD of █████ mL, derived from an inter-participant SD of █████ mL in change from baseline to Week 4, adjusted for 4 repeated measurements and a correlation of █████ between weekly measurements. Assuming a dropout rate of

Statistical Analysis Plan

█████%, approximately 80 evaluable participants per arm are needed. Due to the restricted recruitment into the █████mg dose arm the precision of inference in terms of statistical power will be less than █████% for the comparisons █████mg versus placebo. A participant will be considered evaluable if he/she has a baseline and Week 4 FEV₁ results available. Part 2 will consist of approximately 165 participants.

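### The arm of about 5 participants stays among the primary tests against all placebo, although on the planned totals only about 5 of 80 placebo participants are concurrent with it

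*SAP*

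**What the plan says.** Protocol 9.1 and SAP 4.10.1 place both doses under the Part 2 primary null hypothesis: "The following comparisons will be performed", followed by each dose against placebo. On multiplicity, protocol 9.1 says "No adjustments for multiple testing will be performed". SAP 4.11 gives LS mean differences, standard errors, 95% CIs and p-values for every active arm. SAP 4.12.1 and 4.12.4 reuse the model for average FEV1 and FeNO, so the contrast recurs there.

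The model terms in SAP 4.11 are treatment, week, country, baseline FEV1 and treatment-by-week. The analysis set is the whole FAS (SAP 4.5.2 and 4.10).

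The protocol synopsis and SAP 3.1.2 plan about 5 participants in one dose arm and 80 each in the other dose and placebo. The synopsis says that "the randomisation ratio will change during the study": 2:1 active to placebo while the small arm recruits, then 1:1. The protocol's summary of changes explains the figure of 5: "To reflect number of participants randomised prior to stopping randomisation into the 20 mg arm". That same amendment widened entry. The lower FEV1 limit went from 50% to 40% predicted, the CRP limit from 5 to 10 mg/L, and required controller stability from 3 months to 4 weeks. The requirement for a severe exacerbation in the previous 3 years was dropped.

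Protocol 9.2 and SAP 4.19 acknowledge lower power for the restricted arm. SAP 4.2 describes p-values as nominal and asks for care because multiplicity is uncorrected. Neither document mentions non-concurrent controls.

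**The concern.** Randomisation protects a contrast between participants who could have been allocated to either arm at the same time. Once the small arm closed, no later placebo participant could have been allocated to it. Pooling those participants into its control group mixes the drug effect with any shift in case mix, conduct or placebo response over time. Here there is a specific reason to expect some shift, because entry criteria changed after the arm had closed.

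At stake is a p-value that sits formally among the primary comparisons, together with the dose-response reading it invites. It would rest on about 5 treated participants and a control group drawn mostly from a later period.

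**Working it through.** **Concurrent placebo.** Planned totals are 5, 80 and 80. After closure the two large arms are allocated 1:1 and both end at 80, so they must also have been equal before closure. Let x be the number in each large arm while the small arm was open. The 2:1 ratio of active to placebo gives 5 + x = 2x, so x = 5. Non-concurrent placebo is 80 − 5 = 75, and 75/80 = 94%. This uses the phase-specific ratios in the synopsis and SAP 3.1.2. Protocol 4.1.2 still gives 2:1 for all 165 participants, which does not fit 85 active to 80 placebo and should be reconciled.

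**The plan's own figure.** SAP 4.19 states "73 evaluable participants per treatment arm" and "power using a 1-sided test and 5% significance level to detect a difference of 175 mL". Power, SD and dropout are redacted, so 73 cannot be reproduced independently. (Going from 73 to 80 implies dropout of 1 − 73/80 = 8.75%.) Assuming 80% or 90% power, the SD can be back-solved:

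SD = 175 × √(73/2) / (1.645 + z_power)

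- 80% power: 1057.3 / 2.486 = 425 mL
- 90% power: 1057.3 / 2.926 = 361 mL

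Putting these back returns 73 by construction, which is not a check. They already include the SAP's adjustment for repeated measurements.

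**Precision and power for 175 mL, one-sided 5%.** SE = SD × √v, half-width = 1.96 × SE, power = Φ(175/SE − 1.645). Each range runs from SD 361 to SD 425.

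| Control used | v | SE (mL) | 95% CI half-width (mL) | Power |
|---|---|---|---|---|
| All 80 placebo | 1/5 + 1/80 = 0.2125 | 167–196 | 326–384 | 28–23% |
| All placebo, additive phase factor | 0.30625 | 200–235 | 392–461 | 22–18% |
| 5 concurrent placebo | 1/5 + 1/5 = 0.40 | 228–269 | 448–527 | 19–16% |

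For the middle row, the phase-1 placebo level is the mean of the 10 concurrent placebo and main-dose participants, less half the main-dose effect. Its variance factor is 1/10 + (1/4)(2/80) = 0.10625; adding 1/5 for the small arm gives 0.30625. This assumes the main-dose effect is the same in both phases and ignores the other covariates.

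Unlimited placebo (v = 1/5) would raise power only to 23–29%. The limit is the 5 treated participants.

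**Bias, as an illustration only.** Suppose mean response in non-concurrent placebo is lower by 50 or 100 mL after covariate adjustment. The contrast shifts by 75/80 of that, 47 or 94 mL. One-sided type I error, Φ(bias/SE − 1.645), rises from 5% to 8–9% or 12–14%. A shift the other way would hide an effect. The documents give no estimate of such a shift.

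**The case against.** The best defence is that the plan does not lean on this test. The sample size rests on the main dose and placebo only, the lower power is disclosed, p-values are called nominal, and no visible decision rule uses the small-arm result. An interval wider than ±300 mL against a 175 mL target would mislead few readers. Baseline FEV1 and country are in the model, which addresses part of the widened FEV1 range.

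Much of this stands and keeps the point modest. It does not remove it. The power statement concerns precision, and the caution in SAP 4.2 concerns multiplicity; neither covers bias from non-concurrent controls. The covariates do not address CRP, exacerbation history, controller stability or calendar time.

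Three stronger readings are tempting, and the documents do not support them.

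- A reader might infer that the comparison is not randomised at all. The 5 were randomised, double-blind, alongside placebo; the fault lies in pooling later placebo with the concurrent group.
- A reader might infer that most placebo participants entered under the wider criteria. The small arm closed before protocol 8.0, but the number of placebo participants randomised between those two events is not given.
- A reader might infer that bias has been shown. It has not been measured; only the route for it is open.

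**Conclusion.** The point holds in a limited form. A primary comparison with a p-value is kept for an arm of about 5, against a placebo group that on the planned totals is about 94% non-concurrent, and neither the model nor the analysis set allows for this. Power for 175 mL is about 23–28%, with a 95% CI half-width of 326–384 mL.

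These figures assume 80–90% power for the main comparison and the planned 80 placebo participants. SAP 4.20 records a revision for anticipated closure, so 80 may not be reached. Most of the placebo group would still be non-concurrent once it exceeds about 10, and the power hardly depends on its size.

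The main dose versus placebo comparison is unaffected, because on the planned totals those arms are allocated equally in both phases. This should be changed, but it does not threaten the trial's principal conclusion.

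**What to change.** In SAP 4.10.1 and 4.11, and in protocol 9.1 if it is amended again, take the small arm out of the tested hypotheses and report its FEV1 results descriptively. Apply the same rule to average FEV1 and FeNO. If a model contrast is shown, either add a randomisation-phase factor (small arm open or closed) or restrict the control to placebo randomised while that arm was open. Label it exploratory and give an estimate and 95% CI without a p-value.

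The cost is a change of SAP wording and the loss of one nominal p-value with at most about 28% power under the stated assumptions. The interval also widens, to a half-width of about 392–461 mL with an additive phase factor or 448–527 mL with concurrent placebo only. Descriptive reporting still lets the arm contribute to the dose-response, safety and PK picture.
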